## 1. LIST OF ABBREVIATIONS AND DEFINITION OF TERMS

ACCP	American College of Chest Physicians
AE	Adverse Event
Anti-Xa	Anti-Factor Xa
Anti-IIa	Anti-Factor IIa
aPTT	Activated Partial Thromboplastin Time
C	Celsius
CAT	Cancer-Associated Thrombosis
CCG	CRF Completion Guideline
CFR	Code of Federal Regulations
CL	Total body clearance of the drug
CPA	Conventional Pulmonary Angiogram
CRF	Case Report Form
CSA	Clinical Study Agreement
CT	Computed Tomography
CTC	Common Toxicity Criteria
CTCAE	Common Terminology Criteria for Adverse Events
CTV	Computed Tomography Venography
CU	Compression Ultrasound
CUD	Compression Ultrasound with Doppler
CV	Conventional Venography
DIC	Disseminated Intravascular Coagulation
DVT	Deep Vein Thrombosis
EC	Ethics Committee
EDP	Exposure During Pregnancy
EOS	End of Study
ET	Early Termination
EU	European Union
EudraCT	European Clinical Trials Database
FDA	Food and Drug Administration
FSH	Follicle-Stimulating Hormone
GAG	Glycosaminoglycan
GCP	Good Clinical Practice
HIT	Heparin-Induced Thrombocytopenia
ICH	International Conference on Harmonization
ID	Identification
IEC	Independent Ethics Committee
IIP	Investigator Initiation Package
IND	Investigational New Drug
INR	International Normalized Ratio
IP	Investigational Product
IRB	Institutional Review Board
ITP	Idiopathic Thrombocytopenic Purpura
IU	International Units
IUD	Intra-Uterine Device
IV	Intravenous
LFT	Liver Function Test
LMWH	Low Molecular Weight Heparin
IWRS	Interactive Web Response System
MRV	Magnetic Resonance Venography

MRI	Magnetic Resonance Imaging
NCI	National Cancer Institute
OAC	Oral Anticoagulant
PD	Pharmacodynamic(s)
PE	Pulmonary Embolism
PI	Principal Investigator
PK	Pharmacokinetic
PT	Prothrombin Time
SAE	Serious Adverse Event
SC	Subcutaneous
SCTA	Spiral Computed Tomography Angiography
SOP	Standard Operating Procedure
SRSD	Single Reference Safety Document
TB	Tuberculin
$V_d$	Volume of Distribution
VTE	Venous Thromboembolism
V/Q	Ventilation-Perfusion Scan
tPA	Tissue Plasminogen Activator
US	United States
Xa	Factor Xa

## 2. INVESTIGATORS AND STUDY PERSONNEL

This study will be conducted by qualified Investigators under the sponsorship of Pfizer Inc at approximately 40 investigational site(s) in North America and Europe.

[figure not shown]
## 3. INTRODUCTION

### 3.1. Background

This protocol implements a post-approval clinical commitment originally with Eisai Inc and now between Pfizer Inc., and the Food and Drug Administration (FDA) relating to the dalteparin s NDA 20-287/S-035, “for the extended treatment of symptomatic venous thromboembolism [VTE (proximal deep vein thrombosis [DVT] and/or pulmonary embolism [PE])] to reduce recurrent VTE in subjects with cancer”, hereafter referred to as the “CLOT indication”. The Agency indicated that a post-approval study to investigate the safety and efficacy of dalteparin in a pediatric cancer population requiring anticoagulation was warranted. Following a Type C Meeting with FDA on October 5, 2015, this study now includes both pediatric patients with and without cancer.

This phase II pharmacodynamic (PD) study is intended to provide information to guide the conditions under which dalteparin may be used for the acute treatment and secondary prophylaxis of recurrent VTE in children with or without cancer. Pharmacodynamics of dalteparin is being measured only using the Anti-Factor Xa (Xa) activity and not the drug level in the body. In this study, the PD effect (anti-Xa level) is used as a surrogate for the time course of drug exposure because 1) analytical difficulty in measuring the drug in plasma and 2) the instantaneous drug effect on anti-Xa level. Hence, the study is only characterizing the PD of dalteparin in pediatric subjects with and without cancer.

**Figure 1. Chemical Structure of Dalteparin Sodium**

### 3.2. Rationale

Dalteparin sodium (Fragmin®) is a low molecular weight heparin (LMWH), produced by degradation of heparin, a member of the glycosaminoglycan (GAG) family of biological entities found in the intestinal mucosa. Dalteparin was first approved in the US in December 1994 for primary prophylaxis of DVT in subjects undergoing abdominal surgery. This was followed by approvals for primary prophylaxis of DVT in subjects undergoing hip surgery and in medical subjects with severely restricted mobility during acute illness. Dalteparin sodium is also indicated for the prophylaxis of ischemic complications in unstable angina and non-Q-wave myocardial infarction, when concurrently administered with aspirin therapy.

Dalteparin was approved in 2006 for the extended treatment of VTE in adult patients (age  $\geq 18$  years) with cancer. For these indications, dalteparin has an acceptable safety profile. Further information regarding dosage, safety profile, etc., can be found in the current US Package Insert or local Summary of Product Characteristics, which will serve as the Investigators' Brochure for this study.

Multiple retrospective studies have shown that cancer-associated thrombosis (CAT) is a significant entity previously under recognized and under treated. When compared to subjects without cancer, cancer subjects are far more prone to develop VTE; in fact, VTE may represent the initial presenting finding for an otherwise occult cancer. When compared to cancer-free subjects with symptomatic VTE, cancer subjects with VTE are more prone to recurrence and to treatment-related bleeding complications.

The CLOT study [“Randomized Comparison of *Low* Molecular Weight Heparin (Dalteparin, Fragmin®) versus *Oral* Anticoagulant *Therapy* for Long Term Anticoagulation in Cancer Subjects with Venous Thromboembolism”] was the first multinational prospective randomized clinical trial in a general cancer population to show the superiority of LMWH therapy for secondary prophylaxis compared to standard of care therapy using vitamin K antagonists (oral anticoagulants [OAC]) in cancer subjects with confirmed symptomatic lower extremity DVT, PE, or both. However, the CLOT study did not include pediatric subjects and there is limited information in the literature regarding the proper dosing of dalteparin for treatment of VTE in pediatric subjects with cancer.

The use of LMWHs has been evaluated in several published pediatric studies. In a 1996 report, Massicote et al., described their evaluation of enoxaparin in 25 pediatric subjects in Canada either with VTE or at risk of VTE, and deemed by their physicians to be at risk of bleeding with unfractionated heparin. It was observed that an inverse relationship existed between the subject's age (correlated with body weight) and dosing required to achieve effective anti-Xa inhibition, with “newborns” requiring a greater than 50% increased dose per kg (perhaps due to a larger volume of distribution [ $V_d$ ]).

Likewise, in a 1999 report by Nohe et al., doses of dalteparin in 48 children were shown to be effective (129 $\pm$ 43 anti-Xa International Units (IU)/kg, q24h for treatment; 92 $\pm$ 52 anti-Xa IU/kg, q24h for prophylaxis as recommended in the 7th ACCP Guidelines), with higher dosing required for younger children to achieve the same target anti-Xa level. Risk factors for thrombosis in this cohort included the presence of carcinoma in some of the children.

Dosing with enoxaparin in 173 pediatric thrombosis subjects was also evaluated by Dix et al. and reported in 2000. The authors concluded again, as above, that the use of LMWH in children was “...a safe and effective form of anticoagulation”.

The combination of the published data and recognition that for more than 10 years children worldwide have been treated with LMWH for VTE, outside of the approved indication, supports the safety of the recommended doses of LMWH in children.

#### 4. STUDY OBJECTIVES AND ENDPOINTS

The primary objective of this study is to:

- To determine the PD profiles for treatment doses of dalteparin in pediatric subjects of different ages with or without cancer and VTE, using Anti-Xa levels and a population PD analysis methodology;
- To determine the median dose (IU/kg) required to achieve therapeutic Anti-Xa levels (0.5-1.0 IU/mL) based on subject age and weight.

Secondary objectives will be:

- To assess the proportion of major bleeding events during dalteparin treatment;
- To assess the proportion of minor bleeding events during dalteparin treatment;
- To explore the proportion of objectively documented new or progressive symptomatic VTE during dalteparin treatment;
- To explore the relationships of recurrent VTE and major bleeding events with anti-Xa levels, if data permits;
- To explore the proportions of subjects with progression, regression, resolution or no change in the qualifying VTE during dalteparin treatment;
- To describe the overall safety profile of dalteparin in pediatric subjects of different ages with or without cancer and VTE.
- To assess the proportion of subjects achieving an anti-Xa therapeutic range of 0.5 to 1.0 IU/mL during the Dose Adjustment Phase.

Primary Endpoints:

- Determine the median dose of dalteparin (IU/kg) associated with the achievement of the therapeutic Anti-Xa level (0.5-1.0 IU/mL) among subjects that achieved their therapeutic Anti-Xa level during the dose adjustment phase, for each age cohort group;
- Anti-Xa activity versus time profile following dalteparin treatment will be explored using a population PD analysis methodology. Population PD parameters such as clearance, volume of distribution, absorption rate constant will be estimated based on Anti-Xa levels collected during dose adjustment phase, PD phase and follow-up phase. Age and other relevant covariates will be explored in the population PD analysis.

Secondary Endpoints:

- Proportion of subjects achieving an Anti-Xa therapeutic range of 0.5 to 1.0 IU/mL during the Dose Adjustment Phase (up to 7 days);
- Proportion of subjects with objectively documented, new or progressive symptomatic VTE during dalteparin treatment utilizing the same objective technique performed at Baseline;
- Time to first episode of symptomatic recurrent VTE during dalteparin treatment;

[figure not shown]
- Proportions of subjects with progression, regression, resolution and no change (in comparison to qualifying VTE) during dalteparin treatment;
- Proportion of subjects with major bleeding during dalteparin treatment;
- Proportion of subjects with minor bleeding during dalteparin treatment;
- Relationship between major bleeding event and the Anti Xa level during dalteparin treatment if data permits; Description of subjects' adverse events (AEs) throughout the study period;
- Summary of chemistry, hematology, vital signs and physical examinations.
- Time to first major bleeding events during dalteparin treatment.

## 5. INVESTIGATIONAL PLAN

### 5.1. Overall Study Design and Plan – Description

The study is a 3-month prospective, multicenter, open-label cohort study in North America and Europe to determine twice daily dosing recommendations of dalteparin as a function of age in order to achieve Anti-Xa levels of 0.5 to 1.0 IU/mL at 4 hour ( $\pm$  1 hour) post-dose in children with or without various cancers and requiring anticoagulation for the treatment and secondary prophylaxis of VTE. The study is divided into 3 phases: 1) Dose Adjustment Phase of up to 7 days; 2) PD Phase; and 3) Follow-Up Phase, to complete up to 90 days of treatment for cancer patients and treatment of non-cancer patients should be aligned with the 2012 ACCP Guidelines which suggest a total duration of anticoagulation treatment of between 6 weeks and 3 months rather than shorter or longer durations (Grade 2C), following completion of the PD Phase. Non-cancer patients will be required to remain in the study, however, for the full 3 months to complete all remaining study visits, regardless of dalteparin treatment duration. For non-cancer patients who stop dalteparin treatment prior to 3 months, Anti-Xa and Anti-IIa plasma sampling will not be required after study medication discontinuation.

**Figure 2. Schematic Trial Design**

## 5.2. Discussion of Study Design, Including the Choice of Subjects

This is a multi-center open-label study with no control group. This Phase II PD study is intended to provide information to guide the conditions under which dalteparin may be used for the treatment of acute and secondary prophylaxis of VTE in children with or without cancer. Subjects will be enrolled into the following five age groups:

- 0 to < 8 Weeks;
- $\geq 8$  Weeks to < 2 Years;
- $\geq 2$  Years to < 8 Years;
- $\geq 8$  Years to < 12 Years;
- $\geq 12$  Years to < 19 Years.

The target enrollment is a total of 50 subjects who have viable PD profiles after treatment doses of dalteparin.

### Dose Adjustment Phase:

The Dose Adjustment Phase will begin following the first dose and continue for up to 7 days. During the Dose Adjustment Phase, doses are adjusted according to Anti-Xa levels. The starting doses for the five age groups are as follows:

- 0 to <8 weeks – 125 IU/kg;
- $\geq 8$  weeks to < 2 years– 150 IU/kg;
- $\geq 2$  years to <8 years – 125 IU/kg;
- $\geq 8$  years to <12 years – 125 IU/kg and
- $\geq 12$  years to <19 years – 100 IU/kg.

The first Anti-Xa plasma sample drawn after the initial dose of study drug treatment should be conducted 4 hours  $\pm$  1 hour after the first, second or third dose of study medication per Investigator judgment. Subsequent Anti-Xa plasma samples conducted following dose adjustments will also be drawn at 4 hours  $\pm$  1 hour post-dose, after the first, second or third dose of study medication per Investigator judgment. Doses will be adjusted in increments or decrements of 25 IU/kg in order to achieve target anti-Xa levels (0.5-1.0 IU/mL). All plasma samples should be drawn within the assigned window at each visit, however, if this is not possible, record the actual time the sample is drawn. Plasma samples drawn during the Dose-Adjustment Phase and Follow-Up Phase that deviate outside the 4  $\pm$  1 hr window cannot use the anti-Xa reference range, 0.5-1.0 IU/mL, and should be repeated the next day for both central and local labs. The actual dosing time prior to the repeat plasma sample draw and the actual time of the repeat sample draw must be recorded.

### PD Phase:

Subjects completing the Dose Adjustment Phase will enter into the PD Phase. Dalteparin sodium will be administered subcutaneously every 12 hours  $\pm$  1 hour (no less than 8 hours between doses) with the maintenance therapeutic dose from the Dose Adjustment Phase.

However, if a dose is not able to be delivered every 12 hours  $\pm$ 1 hour, administer the dose (no less than 8 hours between doses) and record the actual dosing time. The PD Phase will last for 1 to 7 days in order to complete two PD samples for each subject (for the central lab, only). Subjects from each age group will be randomized according to a randomization scheme provided by the electronic system, IMPALA, into two different plasma sampling windows: 1 to 3 h and 5 to 8 h or 3 to 5 h and 8 to 12 h until at least 50 subjects provide viable PD Phase Anti-Xa values. All plasma samples should be drawn within the assigned window at each visit, however, if this is not possible, record the actual time the plasma sample is drawn in the Case Report Form (CRF) and repeat it when appropriate at the correct time, if possible.

The plasma sampling times can be spread over the duration of the PD Phase (up to 7 days) to avoid blood volume shifts if necessary. The assignment of the time points to the subjects within each age group will be centrally randomized.

#### **Follow-up Phase:**

After subjects successfully complete the PD Phase, they will enter the Follow-up Phase. During this phase, dalteparin sodium will be administered subcutaneously every 12 hours  $\pm$ 1 hour (no less than 8 hours between doses) with the maintenance therapeutic dose at Visits 5, 6 and 7. However, if a dose is not able to be delivered every 12 hours  $\pm$ 1 hour, administer the dose (no less than 8 hours between doses) and record the actual dosing. One Anti-Xa plasma sample will be collected at 4 hours  $\pm$ 1 hour post-dose at each visit to check if the Anti-Xa level remains within the target therapeutic range. If not, a dose adjustment may be required, per Investigator judgment. All plasma samples should be drawn within the assigned window at each visit, however, if this is not possible, record the actual time the sample is drawn. Plasma samples drawn during the follow up phase that deviate outside the  $4 \pm 1$  hr window cannot use the Anti-Xa reference range, 0.5-1.0, and should be repeated the next day for both central and local labs. The actual dosing time prior to the repeat plasma sample draw and the actual time of the repeat sample draw must be recorded.

For non-cancer patients who stop dalteparin treatment prior to 3 months according to the ACCP Guidelines, Anti-Xa and Anti-IIa plasma sampling will not be required after study medication discontinuation.

Throughout the 3 month study period, the actual times of dosing and anti-Xa blood draw times will be captured on the patient Case Report Form (CRF).

The use of intravenous or intra-arterial cannulas for blood sample collection is not permitted.

### **5.3. Definition of End of Study and Early Discontinuation**

End of study (EOS) is defined as Day 90 ( $\pm$  14 days) after study Baseline. Early Discontinuation from Study Drug: Early discontinuation from study drug treatment will be defined as less than 90 days of study treatment for cancer patients. For non-cancer patients, between 6 weeks and 3 months, rather than shorter or longer durations (Grade 2C), following completion of the PD Phase (2012 ACCP Guidelines) due to: 1) new or recurrent VTE; 2) bleeding necessitating permanent discontinuation of anticoagulant therapy; 3) unexpected permanent discontinuation of anticoagulant therapy; 4) AEs necessitating discontinuation of study drug; 5) withdrawal of consent to participate in the

trial, or 6) inability to achieve therapeutic range during Dose Adjustment Phase. Non-cancer patients will be required to remain in the study, however, for the full 3 months, regardless of dalteparin treatment duration.

#### **5.4. Sponsor's Qualified Medical Personnel**

The contact information for the sponsor's appropriately qualified medical personnel for the study is documented in the study contact list located in the team SharePoint site.

To facilitate access to appropriately qualified medical personnel on study-related medical questions or problems, subjects are provided with a contact card. The contact card contains, at a minimum, protocol and investigational compound identifiers, patient study numbers, contact information for the investigational site, and contact details for a contact center in the event that the investigational site staff cannot be reached to provide advice on a medical question or problem originating from another healthcare professional not involved in the subject's participation in the study. The contact center phone number can also be used by investigational staff if they are seeking advice on medical questions or problems; however, it should only be used in the event that the established communication pathways between the investigational site and the study team are not available. It is therefore intended to augment, but not replace, the established communication pathways between the investigational site and the study team for advice on medical questions or problems that may arise during the study. The contact number is not intended for use by the subject directly, and if a subject calls that number, he or she will be directed back to the investigational site.

### **6. SELECTION OF STUDY POPULATION**

#### **6.1. Number of Subjects**

Subjects, from approximately 40 centers in North America and Europe, will be enrolled into the following five age groups:

- 0 to < 8 Weeks;
- $\geq$  8 Weeks to < 2 Years;
- $\geq$  2 Years to < 8 Years;
- $\geq$  8 Years to < 12 Years;
- $\geq$  12 Years to < 19 Years.

The target enrollment is 50 subjects. Enrollment will continue until 50 subjects have viable PD profiles after treatment doses of dalteparin.

#### **6.2. Inclusion Criteria**

Subjects who meet all of the inclusion criteria and none of the exclusion criteria will be eligible for entry into the study.

Subjects meet inclusion if all of the following are true:

1. Have been objectively diagnosed with a venous thrombotic event documented using one of the following acceptable imaging modalities within 4 days of the Screening Visit:
  - Compression ultrasound with Doppler [CUD];
  - Computed tomography with/without venography [CT/CTV];
  - Magnetic resonance imaging with/without venography [MRI/MRV];
  - Conventional venography [CV];
  - Ventilation-perfusion scan [V/Q] (for pulmonary artery);
  - Spiral CT angiography [SCTA];
  - Conventional pulmonary angiogram [CPA].
2. Are judged clinically to require anticoagulation therapy.
3. Are in the age range of  $\geq 36$  weeks gestation and  $< 19$  years at the Screening Visit.
4. Have given signed informed consent (and assent, as appropriate) to participate prior to the Screening Visit.
5. For cancer patients only, a diagnosis of active malignancy (currently under treatment), other than basal cell or squamous cell carcinoma of the skin.
6. Male subjects able to father children and female subjects of childbearing potential and at risk for pregnancy must agree to use a highly effective method of contraception throughout the study and for at least 28 days after the last dose of assigned treatment.
7. Willing and able to comply with scheduled visits, treatment plan, laboratory tests, and other study procedures.
8. Female subjects of non-childbearing potential must meet at least 1 of the following criteria:
  - a. Achieved post-menopausal status, defined as follows: cessation of regular menses for at least 12 consecutive months with no alternative pathological or psychological cause; (status may be confirmed with/and have) (select one as appropriate) a serum follicle-stimulating hormone (FSH) level confirming the post-menopausal state;
  - b. Have undergone a documented hysterectomy and/or bilateral oophorectomy;
  - c. Have medically confirmed ovarian failure.

### **6.3. Exclusion Criteria**

Subjects are excluded if any one of the following apply:

1. Weight  $\leq 3.0$  kg or  $> 100$  kg at the Screening Visit.

2. Platelet count  $\leq 50,000/\text{mm}^3$  (despite appropriate medical measures to support platelet count).
3. Received OAC therapy within 3 days of the Screening Visit .
4. History of administration of therapeutic doses of LMWH or unfractionated heparin for a period of  $> 4$  days (or  $>8$  doses of LMWH) for the qualifying VTE.
5. Received unfractionated heparin within 3 hours, or LMWH within 12 hours, of the first dose of dalteparin.
6. Acute VTE intervention which includes thrombolytic therapy.
7. Subjects with Mmajor bleeding or bleeding disorders such as Platelet Dysfunction, Protein Deficiency, Disseminated Intravascular coagulation (DIC), Factor Deficiency, Hemophilia, Idiopathic Thrombocytopenic Purpura (ITP) or Von Willebrand Disease at the time of the Screening Visit or an unacceptably high risk of bleeding, at the discretion of the investigator, should not be considered candidates.
8. Major bleeding at the time of the Screening Visit or an unacceptably high risk of bleeding at the discretion of the investigator.
9. Activated partial thromboplastin time (aPTT)  $\geq 5$  seconds above upper limit of normal (ULN), which does not correct to within normal limits upon 1:1 mixing with normal plasma.
10. Prothrombin time (PT)  $\geq 2$  seconds above ULN, and that corrects to within normal limits upon 1:1 mixing with normal plasma.
11. Creatinine clearance  $< 60 \text{ mL}/\text{min}/1.73\text{m}^2$  in subjects  $> 1$  month of age.
12. Uncontrolled hypertension characterized by a sustained systolic pressure or diastolic pressure  $> 99$ th percentile of age- and height-related norms.
13. History of heparin-induced thrombocytopenia (HIT).
14. Any condition in which the investigator feels the subject is unsafe or inappropriate for study participation.
15. Participation in other clinical studies involving investigational drug(s) within the past 30 days.
16. Insufficient subcutaneous tissue to facilitate subcutaneous drug administration.
17. Pregnant female subjects; breastfeeding female subjects; male subjects able to father children and female subjects of childbearing potential who are unwilling or unable to use a highly effective method of contraception as outlined in this protocol for the duration of the study and for at least 28 days after the last dose of assigned treatment.

18. Unable or unwilling to comply with scheduled follow-up visits.

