
Exclusion Criteria:
	
Subjects are excluded if any one of the following apply:
 
 
1. Weight <math>\leq 3.0</math> kg or <math>>100</math> kg at the Screening Visit.
 
2. Platelet count <math>\leq 50,000/\text{mm}^3</math> (despite appropriate medical measures to support platelet count).
 
3. Received oral anticoagulant (OAC) therapy within 3 days of the Screening Visit.
 
4. History of administration of therapeutic doses of Low Molecular Weight Heparin (LMWH) or unfractionated heparin for a period of <math>> 4</math> days (or <math>>8</math> doses of LMWH) for the qualifying VTE.
 
5. Received unfractionated heparin within 3 hours, or LMWH within 12 hours, of the first dose of dalteparin.
 
6. Acute VTE intervention which includes thrombolytic therapy.
 
7. Subjects with major bleeding or bleeding disorders such as Platelet Dysfunction, Protein Deficiency, Disseminated Intravascular coagulation (DIC), Factor Deficiency, Hemophilia, Idiopathic Thrombocytopenic Purpura (ITP) or Von Willebrand Disease at the time of the Screening Visit or an unacceptably high risk of bleeding, at the discretion of the investigator, should not be considered candidates..
 
8. Activated partial thromboplastin time (aPTT) <math>\geq 5</math> seconds above upper limit of normal (ULN), and that corrects to within normal limits upon 1:1 mixing with normal plasma.
 
9. Prothrombin time (PT) <math>\geq 2</math> seconds above ULN, and that corrects to within normal limits upon 1:1 mixing with normal plasma.
 
10. Creatinine clearance <math><60</math> mL/min/1.73m^2 in subjects <math>>1</math> month of age.
 
11. Uncontrolled hypertension characterized by a sustained systolic pressure or diastolic pressure <math>>99</math>th percentile of age- and height-
 

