	
related norms.
 
12. History of heparin-induced thrombocytopenia (HIT).
 
13. Any condition in which the investigator feels the subject is unsafe or inappropriate for study participation.
 
14. Participation in other clinical studies involving investigational drug(s) within the past 30 days.
 
15. Insufficient subcutaneous tissue to facilitate subcutaneous drug administration.
 
16. Pregnant female subjects; breastfeeding female subjects; male subjects able to father children and female subjects of childbearing potential who are unwilling or unable to use a highly effective method of contraception as outlined in this protocol for the duration of the study and for at least 28 days after the last dose of assigned treatment.
 
17. Unable or unwilling to comply with scheduled follow-up visits.
 
(See Section 6.2 for complete listing of Inclusion Criteria and Exclusion criteria).

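### The synopsis and Section 6.3 give opposite mixing-test conditions for the aPTT exclusion, so the same child is eligible under one and excluded under the other

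*Protocol*

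**What the plan says.** Exclusion no. 8 in the Protocol Synopsis applies to an aPTT at least 5 "seconds above upper limit of normal (ULN), and that corrects to within normal limits upon 1:1 mixing with normal plasma". Section 6.3 no. 9 uses the same 5-second threshold but applies to an aPTT "which does not correct to within normal limits upon 1:1 mixing with normal plasma". Both lists exclude a child who meets any single item.

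The PT exclusion is a useful comparison. In both places (synopsis no. 9 and Section 6.3 no. 10) it applies to a PT at least 2 "seconds above ULN, and that corrects to within normal limits upon 1:1 mixing with normal plasma".

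The synopsis list ends by sending the reader to Section 6.2 "for complete listing of Inclusion Criteria and Exclusion criteria". Section 6.2 holds the inclusion criteria and the general rule, "Subjects who meet all of the inclusion criteria and none of the exclusion criteria will be eligible for entry into the study". The exclusion list itself is in Section 6.3. The SAP does not restate eligibility.

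**The concern.** The aPTT rule helps decide which children start treatment-dose dalteparin. As written, two sites could see identical screening results, reach opposite decisions, and each cite the protocol. The study plans about 40 centers and has no data monitoring committee.

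Whichever condition is intended, a site working from the other page makes two kinds of error. Suppose an aPTT that corrects is meant to exclude. A site using Section 6.3 then does not apply the rule to those children, and it refuses children whose aPTT does not correct. If the opposite is meant, a site using the synopsis makes the mirror-image errors.

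**Working it through.** No arithmetic is needed to establish the conflict. It is enough to compare the two texts for a child with aPTT at least 5 seconds above the upper limit of normal, a mixing result, and no other exclusion:

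| Mixing result | Synopsis no. 8 | Section 6.3 no. 9 |
|---|---|---|
| Corrects | Excluded | Not excluded |
| Does not correct | Not excluded | Excluded |

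The two lists disagree in both rows, so they disagree for every such child.

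**Does the protocol settle which version is meant?**

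- The aPTT rule appears once in each form, so counting statements does not decide it.
- The PT rule reads the same way in both lists: exclusion if it corrects. Section 6.3 no. 9 is the only one of the four coagulation statements that goes the other way.
- Section 6.3 no. 7 excludes known bleeding disorders, including "Factor Deficiency, Hemophilia, Idiopathic Thrombocytopenic Purpura (ITP) or Von Willebrand Disease at the time of the Screening Visit". An aPTT rule aimed at values that correct is consistent with that item.
- These points favour the synopsis wording. They are inference, and no text confirms it.

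**Does the protocol say which list governs?** The synopsis pointer treats the body as the complete listing, but it cites Section 6.2 and does not say that the body prevails if the two differ. The body list has 18 items ("18. Unable or unwilling to comply with scheduled follow-up visits") and the synopsis 17 ("17. Unable or unwilling to comply with scheduled follow-up visits").

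**Numbering.** The additional item is Section 6.3 no. 8 (major bleeding or high bleeding risk). From there on, synopsis no. k corresponds to Section 6.3 no. k + 1, for k = 8 to 17. Exclusion no. 9 therefore means PT in the synopsis and aPTT in Section 6.3. A search of screening records by criterion number would mix the two.

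**Separate minor point on platelets.** Section 7.1.1 requires a platelet count on the last day of the Dose Adjustment Phase. In Table 1 the hematology cell for Visit 3 is blank, and Section 9.3.2 lists no hematology. The next scheduled count is at the end of the PD Phase (Section 9.3.3), which lasts 1 to 7 days (Section 5.2). A site that follows Section 7.1.1 has no delay. A site that follows only the schedule takes its first on-drug count 1 to 7 days late, at the latest on Day 7 + 7 = Day 14. The count is delayed, not lost.

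**The case against.** The strongest reply is that the risk is already largely covered. If the rule is meant to catch factor deficiency, known deficiency is excluded by no. 7 in both lists and by footnote 2 of Table 1, which leaves no discretion. The high-bleeding-risk item (Section 6.3 no. 8), the PT rule (no. 10) and investigator judgment (no. 14) add to this. A site that applied both lists would exclude both kinds of child, which errs towards caution. This stands as a limit on the harm. It does not cover a deficiency still undiagnosed at screening, which is where a laboratory screen matters. Nor can discretion make eligible a child wrongly refused under the unintended wording.

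A second reply is that the body governs because the synopsis defers to it. That is a reasonable reading, but no precedence clause supports it, and it leads to the version that conflicts with the body's own PT rule. The item count does not help either. Section 6.3 no. 8 repeats content already in no. 7, and on inclusion criteria the synopsis is the longer list (9 items against 8 in Section 6.2).

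A third reply is that the direction of the correction is uncertain. Because factor deficiency is already excluded by no. 7, a rule for values that do not correct could be a deliberate, different screen. This cannot be ruled out, so the sponsor has to state which condition is meant.

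**Conclusion.** The contradiction is real, and it lies in current operative text. One of the two aPTT statements is wrong as written. It is a drafting error with a safety bearing, and it should be fixed.

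The two lists give opposite decisions for every child with aPTT at least 5 seconds above the upper limit of normal, a mixing result and no other exclusion. The size of that group cannot be estimated from the documents. The error changes no endpoint, sample size or analysis method, and no effect on the bleeding rate is claimed. That the synopsis wording is the intended one is likely but unproven; the finding does not depend on it. The platelet point adds nothing to the rating.

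**What to change.** Issue an amendment or clarification letter that:

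- uses one aPTT condition, in identical words, in synopsis no. 8 and Section 6.3 no. 9. The likely change is to bring Section 6.3 no. 9 into line with the synopsis and the PT rule, once the sponsor confirms that this is the intent;
- corrects the synopsis pointer to name Sections 6.2 and 6.3.

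Then list any enrolled children whose screening aPTT was at least 5 seconds above the upper limit of normal. Identify them by the recorded value, not by criterion number. Safety tests are run at local laboratories, so each site's own upper limit is needed. Section 9.1.8 lists aPTT but no mixing test, so mixing results may have to come from source records. No PT listing is needed, because that rule is consistent.

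Separately, add the platelet count that Section 7.1.1 already requires to the Visit 3 column of Table 1 and to Section 9.3.2.

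The cost is a few lines of text and one listing from an aPTT value already collected, plus a source-record check for any child it identifies. No new test is added.
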